## 2. Objectives

### CIP chapter 7.1 Objectives

*This study is designed as a pre-market clinical study to provide evidence on the safety, performance and usability of the Renamic Neo programmer hardware, software and ECG cable PK-222-L to support regulatory approval, with a focus on requirements of the European Medical Device Regulation (MDR). The study is also intended to identify and evaluate residual risks associated with the use of the Renamic Neo programmer system that remained unrevealed even after risk analysis, risk mitigation and completed validation of the device. The results will be used to update the clinical evaluation of the devices.*

## 3. Investigational Device

### CIP chapter 4.7.1 Renamic Neo hardware and software

*The Renamic Neo programmer system comprises the Renamic Neo hardware, software and the ECG cable PK-222-L. The functional design is highly similar to the predecessor Renamic. Some software features related to PSA functionalities and the graphical user interface (GUI) have been optimized and are described below. The hardware consists of the Renamic Neo, the programmer head (PGH), the battery and the pacing system analyzer (PSA). Several accessories can be used with the programmer to record ECG or to conduct lead positioning checks during implantations. These include ECG cables, patient cables, electrode clips and patient adapters.*

...

## 4. Study Design & Time Course

### CIP chapter

*Patients will be enrolled either for implantation including subsequent pre-hospital discharge or for a follow-up visit only. ICM patients will be included for follow-ups only. As the total study duration is planned for only 3 months different patients will be included for implantation and for follow-up. Patients that have been enrolled in the study and were terminated shall not be included a second time in the study.*

...

**Table 3:** Overview of study procedures

Investigations	Enrollment / Baseline	For patients enrolled before implantation		For patients enrolled after implantation
		Implantation	Pre-hospital discharge	Follow-up
Patient informed consent	x			
Verification of in- and exclusion criteria	x			
Demographics and medical history	x			
Information on implanted IPG, ICD, CRT or ICM, leads (device log)	x*	x		
PSA measurements and evaluation		x		
Device based measurements and evaluation, if applicable		x	x	x
Evaluation of implant interrogation and programming functionality		x	x	x
General assessment of Renamic Neo hardware and software		x	x	x
Evaluation of usability of Renamic Neo system		x	x	x
Data export (connectivity, printing)		x	x	x
Data export of use case data for evaluation at sponsor		x	x	x
Used accessories (including entry in device log)		x	x	x
Battery usage		x	x	x
Adverse event and device deficiency reporting	x	x	x	x
Concomitant medication	x 	x 	x 	x 
Regular termination			x	x

x point in time of study procedure depends if patient is enrolled for implantation use case (includes PHD) or for follow-up use case.

x\* point in time for follow-up cases

x only if related to an AE

## 5. General Statistical Procedures

### 5.1. Descriptive analyses

#### CIP chapter 11.1 Statistical design, method and analytical procedures

For continuous variables descriptive statistics (mean, standard deviation, median, quartiles, minimum, and maximum) will be calculated. For nominal and ordinal variables absolute and relative frequencies will be calculated based on non-missing data. Ordinal variables are described similar as continuous data (minimum, median, quartiles, and maximum) or by absolute and relative frequencies based on non-missing data of each category. Further details will be provided in the separate Statistical Analysis Plan (SAP).

For illustration, see the following standard tables with and without subgroup analyses based on dummy data.

#### Nominal – dichotomous data

Variable (N total = 10)	Category	N non-missing	Absolute frequency	Relative frequency [%]
Gender	Female	9	3	33.3
History of atrial fibrillation	Yes	8	4	50.0

Variable (N total = 10)	Category	Group Type of implanted device	N non-missing	Absolute frequency	Relative frequency [%]
Gender	Female	ICD (N group = 4)	4	1	25.0
		CRT (N group = 4)	4	2	50.0
		All	9	3	33.3
History of atrial fibrillation	Yes	ICD	4	2	50.0
		CRT	4	2	50.0
		All	8	4	50.0

#### Nominal data – more than two categories

Variable (N total = 10)	N non-missing	I N(%)	II N(%)	III N(%)	IV N(%)
NYHA class	8	1 (12.5%)	3 (37.5%)	3 (37.5%)	1 (12.5%)

Variable (N total = 10)	Group Type of implanted device	N non-missing	I N(%)	II N(%)	III N(%)	IV N(%)
NYHA Class	ICD (N group = 4)	3	0 (0.0%)	1 (33.3%)	2 (66.7%)	0 (0.0%)
	CRT (N group = 4)	4	1 (25.0%)	1 (25.0%)	1 (25.0%)	1 (25.0%)
	All	8	1 (12.5%)	3 (37.5%)	3 (37.5%)	1 (12.5%)

Scale / metric data

Variable (N total = 10)	N non- missing	Mean	SD	Min	Lower quartile	Median	Upper quartile	Max
Age [years]	9	56.1	15.9	25.0	50.0	60.0	66.0	77.0
Weight [kg]	8	78.5	13.9	55.0	69.5	78.5	89.0	99.0

Variable (N total = 10)	Group Type of implanted device	N non- missing	Mean	SD	Min	Lower quartile	Median	Upper quartile	Max
Age [years]	ICD (N group = 4)	4	61.8	11.2	50.0	55.0	60.0	68.5	77.0
	CRT (N group = 4)	4	50.3	21.5	25.0	32.5	53.0	68.0	70.0
	All	9	56.1	15.9	25.0	50.0	60.0	66.0	77.0
Weight [kg]	ICD	3	85.0	7.0	77.0	77.0	88.0	90.0	90.0
	CRT	4	76.0	18.5	55.0	62.5	75.0	89.5	99.0
	All	8	78.5	13.9	55.0	69.5	78.5	89.0	99.0

Ordinal data

Identical tables as for metric data but without mean and SD

## 5.2. Inferential analyses

CIP chapter 11.3 Level of significance and the power of the study

*Because there are no pre-specified hypotheses, all analyses will be exploratory.*

...

## 5.3. Significance level

CIP chapter 11.3 Level of significance and the power of the study

*Because there are no pre-specified hypotheses, all analyses will be exploratory. For inferential analyses, a two-sided p-value less than 5% will be considered statistically significant. In accordance to the exploratory approach there will be no adjustment for multiplicity.*

...

## 5.4. Missing Data

CIP chapter 11.11 Handling of missing, unused and spurious data

*For the endpoints, missing data will not be imputed.*

*Free text will be used to clarify other data.*

*Spurious data will be clarified via the query management system, i.e. corrected after approval of an investigator. Remaining outliers will be identified during the review of the data before CDMS closure. In case of a clear evidence of a measurement error, the Statistical Analysis Plan will be updated in order to avoid any bias. Spurious data, which were not clarified by the query process before CDMS freeze or closure, will be indicated. If appropriate, analyses will be performed both with/without such data.*

## 5.5. Exclusion of data from confirmatory data analysis

CIP chapter 11.12 Exclusion of data from the confirmatory data analysis

*No data are documented or analyzed from patients without documented informed consent.*

## 5.6. Subgroups

CIP chapter 11.9 Specification of subgroups

*Potential critical events will be analyzed whether there is any connection to the subgroups IPG, ICD, CRT, or ICM.*

## 5.7. Interim analyses

CIP chapter 11.6 Provision for an interim analysis

*There is one planned interim analyses for internal purposes. Except for safety reasons no investigator is informed about the results and, thus, no bias is expected. There will be no adjustment for multiplicity.*

## 5.8. Software

All analyses will be carried out using validated software, e.g. SAS version 9.4 or upgrades.

## 5.9. CDMS export

### Datasets to be analyzed based on this SAP

Dataset name	Data rows, unique identifier variables except record id	Data rows unique identifier description	Parent CRF In case of embedded log	Notes
enrollment	patient display id full	Patient	n.a.	
baseline	patient display id full	Patient	n.a.	
Medical history	patient display id full	Patient	n.a.	
implantation psa	patient display id full	Patient	n.a.	
general assessments	patient display id full & autom SVTYP	Patient & visit type	n.a.	Visit type: Implantation, pre-hospital discharge follow-up (PHD), regular follow-up after PHD
accessory log details	patient display id full & SVTYP & helpvar model & DIPRGSNR	Patient & visit type & model & programmer serial no.	n.a.	Accessories: Renamic Neo programmer, ECG cable, electrode clip, patient cable, patient adapter
device log details	patient display id full & DIDVTYP	Patient & device type	n.a.	Device type: Pacemaker (single/dual chamber), ICD (single/dual chamber) CRT-P device, CRT-D device, ICM (Insertable Cardiac Monitor) RA lead, RV lead LV lead, VCS lead
adverse event	n.a.	Event	n.a.	
internal adjudication	n.a.	Event	n.a.	
device deficiency	n.a.	Event	n.a.	Investigational device: Renamic Neo Programmer, Renamic Neo Programmer Software, PK-222-L ECG cable
study termination	patient display id full	Patient	n.a.	

### Other Datasets

Dataset name	Data rows, unique identifier variables except record id	Data rows unique identifier description	Parent CRF in case of embedded log	Notes
hospitalization log	n.a.	Event	adverse event	
device accountability details	DIDVTYP & DIDVSNR	Device type & device SNR / ID	n.a.	
deviation patient related	DVSPID	Deviation ID	n.a.	
deviation site related	DVSPID	Deviation ID	n.a.	
deviation third party	DVSPID	Deviation ID	n.a.	
concomitant medication log details	patient display id full & CMTRT & CMSTDT	Patient & trade name & start date	n.a.	Documented in case of an adverse event.

## 6. Specific Study Dates

### 6.1. Enrollment date

*CIP chapter 8.3.6 Point of enrollment and study termination*

*Point of enrollment is the date of signature of the informed consent form by the patient.*

Data file, identifier patient display id full	Variable name	Variable label	Variable level	Nominal values
enrollment	DMICDT i	Patient dated ICF	date	n.a.
data SAR	date enr SAR = DMICDT i	Patient dated ICF	date	n.a.

### 6.2. Implantation date

Data file, identifier patient display id full	Variable name	Variable label	Variable level	Nominal values
Implantation psa baseline	PRIMSTDT i SVSTDT i	Date of implantation Date of baseline assessment	date date	n.a. n.a.
data SAR	date imp SAR 	Date of implantation (excluding spurious data)	date	n.a.

### 6.1. PHD date

Data file, identifier patient display id full & autom SVTYP	Variable name	Variable label	Variable level	Nominal values
general assessments for selection autom SVTYP = Pre-hospital discharge follow-up (PHD)	SVFUSTDT i	Date of follow-up	date	n.a.

Data file, identifier patient display id full	Variable name	Variable label	Variable level	Nominal values
data SAR	date PHD SAR = SVFUSTDT i	Date of PHD	date	n.a.

### 6.1. FU date

Data file, identifier patient display id full & autom SVTYP	Variable name	Variable label	Variable level	Nominal values
general assessments for selection autom SVTYP = Regular follow-up after PHD	SVFUSTDT	Date of follow-up	date	n.a.

Data file, identifier patient display id full	Variable name	Variable label	Variable level	Nominal values
data SAR	date FUP SAR = SVFUSTDT i	Date of regular follow-up after PHD	date	n.a.

### 6.2. Termination date

*CIP chapter 8.3.6 Point of enrollment and study termination*

*Date of regular termination for each patient is the date of discharge from the index hospitalization for implantation cases or the date of follow-up after follow-up completion for follow-up cases.*

Data file, identifier patient display id full	Variable name	Variable label	Variable level	Nominal values
study termination	DSTRDT	Date of termination	date	n.a.
data SAR	Date ter SAR = DSTRDT i	Date of termination	date	n.a.

 IF PRIMSTDT i ≥ SVSTDT i  
 THEN date imp SAR^1 = PRIMSTDT i  
 ELSE date imp SAR -> missing

## 7. Analysis Sets & Subgroups

### 7.1. Analysis Sets

Data file, identifier patient display id full enrollment	Variable name	Variable label	Variable level	Nominal values
enrollment	DMSUBSPS	Patient signed the informed consent personally	nominal	 Yes  No
enrollment	DMRPRSPS	An independent witness signed the informed consent since the patient is unable to write	nominal	 Yes  No
study termination	DSDRPPRO	Please specify Drop-out according to protocol	nominal	 No implantation of an active implantable BIOTRONIK device  Other

Data file, identifier patient display id full & autom SVTYP	Variable name	Variable label	Variable level	Nominal values
general assessments	autom SVTYP	Visit type	nominal	 Implantation  Pre-hospital discharge follow-up (PHD)  Regular follow-up after PHD
	PRSVPRG	Was the Renamic Neo programmer used for the visit	nominal	 Yes  No

Data file, identifier patient display id full	Variable name	Variable label	Variable level	Nominal values
data SAR	analysis set enr SAR 	Enrollment analysis set (patients with Biotronik device and usage of Renamic Neo)	nominal	 Yes  No
data SAR	analysis set imp SAR 	Implantation analysis set (patients with Biotronik device and usage of Renamic Neo during implantation)	nominal	 Yes  No
data SAR	analysis set PHD FUP SAR 	PHD and regular FU analysis set (patients with Biotronik device and usage of Renamic Neo during PHD or FU)	nominal	 Yes  No

The implantation analysis set and the PHD/FUP analysis set are not mutually exclusive, i.e. specific patients can belong to both analysis sets.

 IF (DMSUBSPS = Yes OR DMRPRSPS = Yes) AND date enr SAR not missing AND  
 TIINC01 type ≠ No implantation of an active implantable BIOTRONIK device AND  
 any general assessments per patient with PRSVPRG = Yes  
 THEN analysis set enr SAR = Yes  
 ELSE analysis set enr SAR = No

 IF analysis set enr SAR = Yes AND  
 any general assessments per patient with (PRSVPRG = Yes AND autom SVTYP per patient = Implantation)  
 THEN analysis set imp SAR = Yes  
 ELSE analysis set imp SAR = No

 IF analysis set enr SAR = Yes AND  
 any general assessments per patient with  
 ([PRSVPRG = Yes AND autom SVTYP = Pre-hospital discharge follow-up (PHD)] OR  
 [PRSVPRG = Yes AND autom SVTYP = Regular follow-up after PHD])  
 THEN analysis set FUP SAR = Yes  
 ELSE analysis set FUP SAR = No

Subgroups

Data file, identifier patient display id full & DIDVTYP	Variable name	Variable label	Variable level	Nominal values
device log details	helpvar device type	hidden technical field: Short name for General type of device	nominal	
 
○ CRT
 
○ CRT-P
 
○ ICD
 
○ ICM
 
○ IPG
 

Data file, identifier patient display id full	Variable name	Variable label	Variable level	Nominal values
data SAR	subgroup device type SAR 	Subgroup type of device	nominal	
 
○ CRT
 
○ CRT-P
 
○ ICD
 
○ ICM
 
○ IPG
 

 Patient-specific type of device data for helpvar device type not missing  
subgroup device type SAR = helpvar device type

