8.3.6 Point of enrollment and study termination

Point of enrollment is the date of signature of the informed consent form by the patient.

Date of regular termination for each patient is the date of discharge from the index hospitalization for implantation cases or the date of follow-up after follow-up completion for follow-up cases.

In case of premature termination the following rules apply:

- In case of withdrawal of a patient's consent, the date of study termination shall be the date of withdrawal of consent.
- If patient is lost to follow-up, the date of study termination shall be the day of the last contact of the site study team (e.g. investigator or study nurse) with the patient
- If the implantation is not performed successfully due to any reasons the date of study termination shall be the date of the unsuccessful implantation attempt if another attempt is not planned within the following 2 weeks.
- In case of patient death, the date of study termination shall be the date of death.
- In case the patient is terminated prior to study specific procedures because a violation of an inclusion/exclusion criterion was discovered the date when the violation was discovered shall be the date of termination.

Study related procedures and documentation shall end at the day of study termination for the respective patient. However, all adverse device effects will be followed for up to 2 weeks after study termination of the respective patient.

[REDACTED]

[REDACTED]

[REDACTED]

[REDACTED]

[REDACTED]

[REDACTED]

[REDACTED]

[REDACTED]

[REDACTED]

[REDACTED]

[REDACTED]

[REDACTED]

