## 8. Data for a CONSORT diagram and “study realization”

### 8.1. Analysis set

Unless otherwise specified, all analyses are performed for the enrollment analysis set.

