### 8.2. Enrollment

- Date of FPI
- Date of LPI
- Number of patients
- Number of patients per site

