#### Exclusion criteria

Data file, identifier patient display id full	Notes	Variable name	Variable label	Variable level	Nominal values
enrollment	descriptive	TIEXC01	Patient is implanted with a Stratos pacemaker	nominal	 Yes  No
		TIEXC02	Patient is pregnant or breastfeeding	nominal	 Yes  No
		TIEXC03	Patient is less than 18 years old	nominal	 Yes  No
		TIEXC04	Patient is planned for implant exchange or upgrade	nominal	 Yes  No

 analysis set enr SAR = Yes

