### 8.3. Termination

- Date of FPO
- Date of LPO

Data file: Identifier patient display id full	Notes	Variable name	Variable label	Variable level	Nominal values
termination	descriptive	DSRTRM	Regular study termination	nominal	o Yes o No
termination	Descriptive for DSRTRM = No	DSETRREA	Reason for early study termination	nominal	o Patient moved away from investigational center o Patient is lost to follow-up o Patient withdrew consent to study participation o Patient death o Drop-out according to protocol o Enrollment failure

Data file: Identifier patient display id full	Notes	Variable name	Variable label	Variable level	Nominal values
enrollment	Case case listing for DSETRREA =	DMICDT i	Patient: Date of informed consent signature	date	n.a.
termination	Drop-out according to protocol	DSTRDT i	Date of study termination	date	n.a.
		DSDRPPRO	Reason for early study termination	nominal	o No implantation of an active implantable BIOTRONIK device o Other
		CODRPPRO	Please specify Drop-out according to protocol - Other	text	...

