### 8.4. Fu duration

The FU duration has to be analyzed separately for the implantation and follow-up analysis set.

Data file: Identifier patient display id full	Notes	Variable name	Variable label	Variable level	Nominal values
data SAR	descriptive and cumulative sum		FU duration SAR 	scale	n.a

 analysis set imp SAR = Yes

 analysis set FUP SAR = Yes

 FU duration SAR = DSTRDT - DMICDT

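### The SAP's enrollment analysis set requires use of the Renamic Neo, so the enrollment and termination outputs omit patients who consented but left before any use

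*SAP*

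**What the plan says.** **When a patient is enrolled.** Protocol 8.3.6: "Point of enrollment is the date of signature of the informed consent form by the patient". SAP 6.1 repeats this and sets the analysis variable from the consent date: "date enr SAR = DMICDT i".

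**Who is in the enrollment analysis set.** SAP 7.1, footnote 2, joins four conditions by AND: consent signed by the patient or by a witness; enrollment date present; a clause on the variable TIINC01 type; and "any general assessments per patient with PRSVPRG = Yes". PRSVPRG records whether the Renamic Neo was used at the visit.

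**Where the set is applied.** SAP 8.1, on the CONSORT data: "Unless otherwise specified, all analyses are performed for the enrollment analysis set". Section 8.2 then asks for first and last patient in, the number of patients, "Number of patients per site" and the inclusion and exclusion tables. Section 8.3 asks for first and last patient out, regular or early termination and the reasons. The reason list ends with "Drop-out according to protocol o Enrollment failure" (the lone letter is an option bullet), and there is a case listing for the first of these two. Neither section names a different set. Section 8.4 does: "The FU duration has to be analyzed separately for the implantation" and follow-up sets. Section 8.5 also names the implantation and PHD/follow-up sets.

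**Exits before use that the protocol foresees.** Section 11.4 gives early withdrawal as an example. Section 8.3.5.3 describes an eligibility violation, or no implant received, found before any measurement, to be recorded on the termination form. Section 9.3 ends participation if the implantation is not completed within 2 weeks. Sections 8.1.6 and 11.4 replace patients who leave before use.

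**The concern.** A set called *enrollment* that depends on device use contradicts the definition of enrollment in both documents, and it feeds the outputs whose purpose is to account for everyone enrolled. A reader of the report would take the number of users for the number enrolled and would see no loss between consent and first use. Because leavers before use are replaced, the consented and used numbers differ as soon as there is one such patient.

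Section 8.3 also works against itself. It plans a listing of drop-outs according to protocol, yet Protocol 8.3.5.3 describes these as patients found before any measurement, and the set mostly or wholly removes them. The eligibility tables have the same weakness: patients whose violation was caught before use are missing from them.

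At stake is complete patient accounting in a report meant to support regulatory approval. The endpoint results are not at stake.

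**Working it through.** No figure in the plan measures this point, so the check is a trace of the rule.

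**1. Does another section widen the population?** No. The conditions in 8.3 (early termination; reason equal to drop-out according to protocol) select rows inside the default set. The sets named in 8.4 and 8.5 are defined in footnotes 3 and 4, and both require membership of the enrollment analysis set, so they are narrower. SAP 5.5, quoting Protocol 11.12, gives lack of documented consent as the only exclusion.

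**2. Footnote 2 applied to typical patients,** all with documented consent and a consent date:

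| Course | Any visit with PRSVPRG = Yes | In set |
|---|---|---|
| Withdraws soon after consent (Protocol 11.4) | No | No |
| Violation or no implant, found before use (8.3.5.3) | No | No |
| Implantation never attempted within 2 weeks (9.3) | No | No |
| Follow-up done with the Renamic Neo | Yes | Yes |
| Implantation fails after the Renamic Neo was used | Yes | Yes, as written |
| Withdrawal or death after use at implantation | Yes | Yes |

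All three exits before use are removed. Exits after use remain.

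**3. The TIINC01 type clause.** SAP 8.2 gives this variable two values: planned for de novo implantation, or already implanted. Footnote 2 compares it with a no-implantation value that belongs to another variable, DSDRPPRO. The inequality is therefore always true, and the use condition does the excluding in step 2.

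**4. Size, by assumption.** With 120 users (the protocol's approximate enrollment) and d leavers before use, the consented number is 120 + d and the share not shown is d / (120 + d). The documents give no value for d.

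| d (assumed) | Consented | Reported as enrolled | Not shown |
|---|---|---|---|
| 0 | 120 | 120 | 0% |
| 3 | 123 | 120 | 3/123 = 2.4% |
| 6 | 126 | 120 | 6/126 = 4.8% |
| 12 | 132 | 120 | 12/132 = 9.1% |

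**5. Sample size statements.** These count use cases and do not depend on the set. With X binomial (n, 0.05), the probabilities of at least 1, 2 and 3 events are 92.3%, 72.1% and 46.0% for n = 50, and 99.4%, 96.3% and 88.2% for n = 100. They agree with Protocol 11.2 and stay as they are.

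**The case against.** **The label is open about use.** SAP 7.1 states in the set's label that it covers patients with a device and usage of the Renamic Neo. This stands as a mitigation for a reader who sees the label. It does not turn a count of users into a count of patients enrolled as both documents define enrollment.

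**The study follows use cases.** It is uncontrolled and exploratory, it replaces leavers before use, and Protocol 11.4 on that definition expects no drop-outs. Use-based denominators are right for the endpoint chapters, and attrition before use biases no comparison. That all stands. But the protocol's expectation rests on not counting these patients, and it does not say that none will occur. A CONSORT diagram is where they should appear.

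**Part of the information is elsewhere.** Eligibility violations that are protocol deviations are reported under Protocol 14.2. This covers one route in part, and it does not replace a flow diagram.

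A reader might also infer three stronger points that the documents do not support:

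- *The listing of drop-outs according to protocol must be empty.* Protocol 8.3.5.3 speaks of measurements and PRSVPRG of use at the visit; the documents do not equate the two. A failed implantation after PSA use has no code of its own in the reason list and may be entered under this reason as no implantation.
- *The sponsor's decision on stopping under Protocol 20.1 would be misinformed.* That is a decision during conduct, no drop-out rate is defined, and nothing ties it to this table. The SAP serves the final report, and termination forms are completed in any case.
- *Device deficiencies that prevent all use would drop out of SAP chapters 10 and 11.* This depends on such a visit being coded as not used, which no document says. Sites hold 2-3 systems, so a substitute Renamic Neo is plausible.

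**Conclusion.** The point holds for SAP 8.2 and 8.3. As written, these sections report users as enrolled patients and omit every early termination before first use. The 8.3 listing would miss most or all of the patients that Protocol 8.3.5.3 describes.

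The size is the number of leavers before use, which is unknown. With none there is no error; the 2.4% to 9.1% above rests on assumed counts. No endpoint rate and no sample size figure changes. The conclusion assumes only that PRSVPRG is not coded Yes for a patient who left before the programmer was used. It should be corrected because a stated rule gives a wrong enrolled count in a situation that the protocol foresees, and the remedy is small.

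It is also tempting to treat the TIINC01 type clause as a slip that can be deleted without effect. That is true of the literal text only. DSDRPPRO is among the inputs listed in SAP 7.1, and the label refers to patients with a device, which suggests that DSDRPPRO was meant. If so, a failed implantation after PSA use that is coded as no implantation would leave the set, so the wording decides whether that patient counts in the chapter 10 denominator.

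**What to change.** 1. Define an all-consented set, `(DMSUBSPS = Yes OR DMRPRSPS = Yes) AND date enr SAR not missing`, and run SAP 8.2 and 8.3 on it.
2. Show the step from consented to used in the CONSORT diagram, with the reasons for leaving.
3. Rename the present set, for example *Renamic Neo use set*, and keep it for the use-based chapters.
4. In the renamed set, reconcile the TIINC01 type clause with the label and the listed DSDRPPRO input, and state whether a failed implantation after PSA use belongs to the set. Do not simply delete the clause.

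The cost is a SAP revision and minor reprogramming. The enrollment and termination datasets are already among the exports in SAP 5.9, so no new data are needed. Reported attrition may look slightly less favourable.
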